#### 8.2.1.8. CPK elevations and rhabdomyolysis

CPK elevations have been observed in patients who received cobimetinib monotherapy, as well as in patients administered cobimetinib in combination with other agents. The majority of CPK elevations reported were asymptomatic, non-serious, and resolved with or without study drug

interruption. One event of rhabdomyolysis was reported in the Phase III Study GO28141 (cobimetinib + vemurafenib), and rhabdomyolysis has been reported in postmarketing experience. In Study GO28141, CPK elevations was reported as an AE more frequently in patients treated with cobimetinib + vemurafenib (32.4% all grades, 11.3% Grade 3 events) than with placebo + vemurafenib (8.1% all grades, 0% Grade 3 events).

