## 8.4.2.11. Immune-related Myositis

Myositis or inflammatory myopathies are a group of disorders sharing the common feature of inflammatory muscle injury; dermatomyositis and polymyositis are amongst the most common disorders. Initial diagnosis is based on clinical (muscle weakness, muscle pain, skin rash in dermatomyositis). biochemical (serum creatinine-kinase increase). and (electromyography/MRI) features, and is confirmed with a muscle-biopsy. One etiology of myositis is immune-mediated, which is the current concern with atezolizumab.

It is recommended that atezolizumab should be withheld for moderate or severe (Grade 2 or 3) immune-related myositis and permanently discontinued for recurrent severe or life-threatening myositis (recurrent Grade 3 and Grade 4). Please refer the patient to rheumatologist and/or neurologist and consider muscle biopsy and supportive measures as clinically indicated. Corticosteroids treatment with 1-2 mg/kg/day IV methylprednisolone or higher-dose bolus if severely compromised (weakness severely limiting mobility, cardiac function, respiratory function, dysphagia) and/or additional immunosuppressive agents should be administered for ≥ Grade 2 events or if the event does not improve after initial corticosteroids. Please refer to the table below for detailed management guidelines for immune-mediated myositis.

Management Guidelines for Immune-Related Myositis:

Event	Management
Immune-related Myositis	Continue atezolizumab
Grade 1	

Refer patient to a rheumatologist or neurologist

Initiate treatment per institutional guidelines

Immune-related Myositis Grade 2	
 
Initiate treatment per institutional guidelines
 
Withhold atezolizumab for up to 12 weeks after event onset and contact the Study Chair
 
Refer patient to a rheumatologist or neurologist
 
Initiate treatment per institutional guidelines
 
Consider treatment with corticosteroid equivalent to 1-2 mg/kg/day IV methylprednisolone and convert to 1-2 mg/kg/day oral prednisone or equivalent upon improvement
 
If corticosteroids are initiated and event does not improve within 48 hours after initiating corticosteroids, consider adding an immunosuppressive agent.
 
If event resolves to Grade 1 or better, resume atezolizumab
 
If event does not improve to Grade 1 or better while withholding atezolizumab, permanently discontinue atezolizumab and contact the Study Chair.
 

Event	Management

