For Grade 4 CPK elevations that are asymptomatic and deemed not clinically significant	
 
Interrupt cobimetinib and atezolizumab treatment.
 
If improved to Grade ≤ 3 within 4 weeks, restart cobimetinib at a dose reduced by 20 mg, if clinically indicated.
 
If CPK elevations do not improve to Grade ≤3 within 4 weeks following dose interruption, permanently discontinue cobimetinib treatment.
 
Resumption of atezolizumab may be considered in patients who are deriving benefit.
 
Interrupt cobimetinib and atezolizumab treatment.
 
If severity is improved by at least one grade and symptoms resolve within 4 weeks, restart cobimetinib at a dose reduced by 20 mg, if clinically indicated.
 
				
For Grade 4 CPK elevations that are asymptomatic and deemed not clinically significant  Rhabdomyolysis or symptomatic CPK	
 
Interrupt cobimetinib and atezolizumab treatment.
 
If improved to Grade ≤ 3 within 4 weeks, restart cobimetinib at a dose reduced by 20 mg, if clinically indicated.
 
If CPK elevations do not improve to Grade ≤3 within 4 weeks following dose interruption, permanently discontinue cobimetinib treatment.
 
Resumption of atezolizumab may be considered in patients who are deriving benefit.
 
Interrupt cobimetinib and atezolizumab treatment.
 
If severity is improved by at least one grade and symptoms resolve within 4 weeks, restart cobimetinib at a dose reduced by 20 mg, if clinically indicated.
 
If rhabdomyolysis or symptomatic CPK elevations do not improve within 4 weeks,
 
				
For Grade 4 CPK elevations that are asymptomatic and deemed not clinically significant	
 
Interrupt cobimetinib and atezolizumab treatment.
 
If improved to Grade ≤ 3 within 4 weeks, restart cobimetinib at a dose reduced by 20 mg, if clinically indicated.
 
If CPK elevations do not improve to Grade ≤3 within 4 weeks following dose interruption, permanently discontinue cobimetinib treatment.
 
Resumption of atezolizumab may be considered in patients who are deriving benefit.
 
Interrupt cobimetinib and atezolizumab treatment.
 
If severity is improved by at least one grade and symptoms resolve within 4 weeks, restart cobimetinib at a dose reduced by 20 mg, if clinically indicated.
 
If rhabdomyolysis or symptomatic CPK elevations do not improve within 4 weeks, permanently discontinue cobimetinib treatment
 
				

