## e. Assessment of Severity of Adverse Events

The adverse event severity grading scale for the NCI CTCAE v5.0 will be used for assessing adverse event severity. Below Table should be used for assessing severity for adverse events that are not specifically listed in the NCI CTCAE.

Grade	Severity
1	Mild; asymptomatic or mild symptoms; clinical or diagnostic observations only; or intervention not indicated
2	Moderate; minimal, local, or non-invasive intervention indicated; or limiting age-appropriate instrumental activities of daily living a
3	Severe or medically significant, but not immediately life-threatening; hospitalization or prolongation of hospitalization indicated; disabling; or limiting self-care activities of daily living b,c
4	Life-threatening consequences or urgent intervention indicated d
5	Death related to adverse event d

NCI CTCAE = National Cancer Institute Common Terminology Criteria for Adverse Events.

Note: Based on the most recent version of NCI CTCAE (v5.0), which can be found at: http://ctep.cancer.gov/protocolDevelopment/electronic applications/ctc.htm

- a. Instrumental activities of daily living refer to preparing meals, shopping for groceries or clothes, using the telephone, managing money, etc.
- b. Examples of self-care activities of daily living include bathing, dressing and undressing, feeding oneself, using the toilet, and taking medications, as performed by patients who are not bedridden.
- c. If an event is assessed as a "significant medical event," it must be reported as a serious adverse event
- d. Grade 4 and 5 events must be reported as serious adverse events

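### For an event judged immune-related myositis Grade 1 with muscle symptoms and raised CPK, the myositis table and the CK/CPK table give opposite atezolizumab instructions; steroid wording for Grade 2 myositis also differs between narrative and table

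*Combined protocol and SAP*

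**What the plan says.** **Myositis, Section 8.4.2.11.** The initial diagnosis rests on several kinds of feature: "clinical (muscle weakness, muscle pain, skin rash in dermatomyositis"), "biochemical (serum creatinine-kinase increase") and electromyography or MRI findings, with confirmation by muscle biopsy. An immune-mediated cause is described as one etiology among several. In the management table the Grade 1 row begins "Continue atezolizumab", adds a specialist referral and leaves treatment to institutional guidelines. The table gives no instruction on cobimetinib.

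**Grade 2 steroids, same section.** The narrative says that corticosteroids and/or additional immunosuppressive agents "should be administered for ≥ Grade 2 events or if the event does not improve after initial corticosteroids", and then refers the reader to the table for detail. The Grade 2 row says "Consider treatment with corticosteroid equivalent to 1-2 mg/kg/day IV methylprednisolone", and its next steroid step applies only if steroids have been started. The Grade 3 and Grade 4 rows tell the site to initiate them.

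**CK/CPK elevation, Section 8.5.** The block is headed for cobimetinib or atezolizumab. Dosing stays unchanged for elevations up to Grade 3 that are asymptomatic and not clinically significant. A separate row covers rhabdomyolysis or symptomatic CPK elevation. It names no grade, and its action is "Interrupt cobimetinib and atezolizumab treatment".

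**The concern.** A site holding both tables can reach opposite atezolizumab decisions for one event, and the protocol does not say which decision is correct. The event is foreseeable. CPK is scheduled on Day 1 of every cycle (Section 6), CPK elevation is a listed cobimetinib toxicity (Sections 8.2 and 8.2.1.8), and myositis is an atezolizumab event of special interest (Section 16.4).

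The trial is multicenter, and the adverse event profile is a secondary endpoint (Section 2). If sites follow different passages, atezolizumab and cobimetinib exposure and the recorded interruptions will vary for reasons unrelated to the patient. The Grade 2 steroid wording matters for a related reason. Under Section 8.5, once atezolizumab is withheld and steroids are started for an atezolizumab-related toxicity, they must be tapered over at least 1 month before atezolizumab can resume. Whether steroids are expected or optional therefore bears on when dosing restarts.

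**Working it through.** The plan states no figure on this point and no formula applies. The check sets the instructions side by side.

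**Step 1. Which events meet both tables?**

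| Event in a cobimetinib-arm patient | Section 8.4.2.11 table | Section 8.5 CK/CPK block | Conflict on atezolizumab? |
|---|---|---|---|
| Muscle symptoms and raised CPK, not judged immune-related myositis | Does not apply | Interrupt both drugs | No |
| Judged immune-related myositis Grade 1, raised CPK up to Grade 3, no symptoms, not clinically significant | Continue atezolizumab | No change to either drug | No |
| Judged immune-related myositis Grade 1, raised CPK, muscle symptoms | Continue atezolizumab | Interrupt both drugs | **Yes** |
| Judged immune-related myositis Grade 2 or 3, raised CPK, muscle symptoms | Withhold atezolizumab | Interrupt both drugs | Not on the initial hold |

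The direct contradiction is confined to the third line.

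**Step 2. Can Grade 1 myositis have symptoms?** Section 8.4.2.11 calls Grades 2 and 3 moderate or severe, so Grade 1 lies below moderate, and the Grade 1 row is not limited to asymptomatic cases. The severity scale in Section 17.2.2(e) describes Grade 1 as "Mild; asymptomatic or mild symptoms; clinical or diagnostic observations only; or intervention not indicated". That scale is meant for events not listed in CTCAE, and the documents do not show whether myositis is listed, so it supports the reading without settling it.

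**Step 3. Does anything resolve the overlap?** The CK/CPK general guidance asks sites to look for cardiac causes, rhabdomyolysis, exertion, trauma and intramuscular injection. It does not mention immune-related myositis or refer to Section 8.4.2.11. The myositis text does not refer to the CK/CPK block. Immune-related cases are not excluded from that block, whose heading includes atezolizumab. No precedence rule is given.

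**Step 4. Does the choice of table matter later?** Under the symptomatic CPK row, cobimetinib ends permanently if there is no improvement within 4 weeks, and Section 8.6 then allows atezolizumab to continue alone. Under the Grade 2 and 3 myositis rows, atezolizumab ends permanently if the event does not return to Grade 1 while the drug is withheld (up to 12 weeks), and Section 8.6 then takes the patient off both drugs. So even where the initial hold agrees, the two passages can lead to different discontinuations.

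**Step 5. Grade 2 steroids.** The narrative directs that steroids and/or immunosuppressants be given. The table asks the site to consider steroids and makes the next step conditional on having started them. Because the Grade 3 and 4 rows use directive wording, the softer Grade 2 wording is a different instruction from the narrative's.

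**The case against.** The strongest reply is that mild muscle pain with a raised CK is not yet immune-related myositis. Section 8.4.2.11 also lists electromyography or MRI features and biopsy confirmation, and treats the immune-mediated form as one cause among several. Until that judgement is made, only the CK/CPK row applies. This stands. A reader might infer that every cobimetinib patient with mild muscle pain and raised CK is told both to continue and to interrupt atezolizumab. The documents support that only once the event is judged immune-related myositis Grade 1.

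Section 8.4.2.11 sits in the atezolizumab part of Section 8, with cobimetinib modifications placed in Section 8.5. This also stands: its silence on cobimetinib is not an error in itself. It does not remove the overlap, because the CK/CPK block instructs on both drugs.

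On steroids, a reader might infer that the narrative makes them mandatory at Grade 2. It does not go that far. The wording is a recommendation, allows steroids and/or other immunosuppressants, and sends the reader to the table for detail. The firmness still differs, and pointing to the table is not a statement that the table prevails.

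Finally, a reader might try to count the patients. Section 8.2.1.8 gives CPK elevation in patients "treated with cobimetinib + vemurafenib (32.4% all grades, 11.3% Grade 3 events"), and 0.324 × 33 = 10.7 patients at the maximum arm size. An assumed symptomatic share of 10% to 40% would make that 1.1 to 4.3. This does not count the patients at issue. The rate comes from a combination with vemurafenib, which is not given here, and the symptomatic share is not in the documents. The product also counts symptomatic CPK elevations, not events that are in addition judged immune-related myositis Grade 1.

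**Conclusion.** Both inconsistencies are in the current text, and both are narrow. The first yields opposite atezolizumab instructions for one defined event: immune-related myositis Grade 1 with muscle symptoms and raised CPK in the cobimetinib arm. It rests on reading the symptomatic CPK row as written, with no grade threshold and a heading that includes atezolizumab, and on Grade 1 myositis being able to include symptoms. The second is a difference in the firmness of the Grade 2 steroid wording within Section 8.4.2.11.

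The number of patients affected cannot be derived from the documents. Sample size, type I error and power are not affected, and no effect on the 16-week PFS endpoint is shown. The consequence is that sites may handle the same safety event differently, with knock-on differences in exposure and in the reported safety profile. Because a site cannot both continue and interrupt a drug, this should be corrected even if the event is uncommon.

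**What to change.** Reconcile Section 8.4.2.11 with the CK/CPK rows of Section 8.5:

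- State which passage governs when an event meets both, and what it says for atezolizumab and for cobimetinib.
- Add a cross-reference in each section to the other.
- Use the same wording for Grade 2 corticosteroids in the Section 8.4.2.11 narrative and table.

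The clinical leads choose the rule; this review takes no view on which instruction is right. The cost is a wording amendment to two sections, with the IRB approval at each institution that Section 22.2 requires. It adds no tests, visits or patients, and the statistical design does not change.

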# 8.5. Dose Modifications/ Delays and Toxicity Management

# **Atezolizumab** ☐ There will be no dose reduction for Atezolizumab in this study. • If atezolizumab is withheld and corticosteroids are initiated for an atezolizumab-related toxicity, corticosteroids must be tapered over ≥ 1 month to ≤ 10 mg/day oral prednisone or equivalent before atezolizumab can be resumed. Atezolizumab may be withheld for a period of time up to 12 weeks to allow for corticosteroids to be reduced to ≤ 10 mg/day oral prednisone or equivalent. If Atezolizumab is held because of AEs for > 12 weeks beyond the scheduled date of infusion, the patient will be discontinued from Atezolizumab and will be followed for

# Resumption of atezolizumab may be considered in patients who are deriving benefit and have fully recovered from the immune-related event. Patients can be rechallenged with atezolizumab only after approval has been documented by both the investigator (or an appropriate delegate) and the Medical Monitor.

- Dose interruptions for reasons other than toxicity, such as surgical procedures, may be allowed. The acceptable length of interruption will be at the discretion of the Protocol Chair.
- Patients should be assessed clinically (including review of laboratory values) for toxicity prior to, during, and after each infusion. If unmanageable toxicity due to Atezolizumab occurs at any time during the study, treatment with Atezolizumab should be discontinued.

## Cobimetinib

- All dose modifications should be based on the worst preceding toxicity. Once a dose has been reduced it will not be increased at a later time even if there is no toxicity. Patients who require dose reductions of Cobimetinib past the lowest dose level will be discontinued from study drugs treatment.
- If a patient requires a dose delay of > 28 consecutive days from the intended day of the next scheduled dose of Cobimetinib, due to study related interventions, then the patient must be discontinued from the study treatment.
- Patients that require a dose delay of > 28 days due to a cause unrelated to study participation will have the opportunity to continue study if deemed eligible to do so by the Protocol Chair of the study.
- Patients who discontinue from the study for a study-related adverse event (AE) or an abnormal laboratory value must be followed at least once a week for 4 weeks and subsequently at 4-week intervals, until resolution or stabilization of the event, whichever comes first, except specifically mentioned.

	Cobimetinib dose level reductions			
Starting dose	First reduction	Second reduction	Third reduction	
60 mg	40 mg	20 mg	Discontinue	

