
treatment

Intercurrent illness or condition that would, in the judgment of the treating investigator, affect assessment of clinical status to a significant degree or require discontinuation of study

- At subject's own request. Note: The reason for discontinuation from the study must be documented. These patients will be included in the overall evaluation of safety and response if any protocol therapy was administered prior to withdrawal
- Study is closed for any reason (e.g. new information shows that the patient's welfare would be at risk if she continued study treatment)
- General or specific changes in the participant's condition render the participant unacceptable for further treatment in the opinion of the treating investigator
- □ Patients that require a dose delay of > 28 days. If the delay is due to a cause unrelated to study participation, the patient will have the opportunity to continue study if beyond the first 8 weeks of treatment, if clinical benefit is seen, and if deemed eligible to do so by the Protocol Chair of the study
- ☐ If the patient requires dose reduction below dose level -1, the patient should be discontinued from the study unless deemed to have clinical benefit that would outweigh the risk. A discussion with the Protocol Chair should be carried out prior to final decision on discontinuation

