<sup>a Atezolizumab may be withheld for a longer period of time (i.e., > 12 weeks after event onset) to allow for corticosteroids (if initiated) to be reduced to the equivalent of ≤ 10 mg/day oral prednisone. The acceptable length of the extended period of time must be agreed upon by the investigator and the Study Chair.

b If corticosteroids have been initiated, they must be tapered over ≥ 1 month to the equivalent of ≤ 10 mg/day oral prednisone before atezolizumab can be resumed.

eResumption of atezolizumab may be considered in patients who are deriving benefit and have fully recovered from the immunerelated event. Patients can be re-challenged with atezolizumab only after approval has been documented by both the investigator (or an appropriate delegate) and the Study Chair.

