## Idasanutlin

- All dose modifications should be based on the worst preceding toxicity. Once a dose has been reduced it will not be increased at a later time even if there is no toxicity. Patients who require dose reductions of Idasanutlin past the lowest dose level will be discontinued from study drugs treatment.
- If a patient requires a dose delay of > 28 consecutive days from the intended day of the next scheduled dose of Idasanutlin, due to study related interventions, then the patient must be discontinued from the study treatment.
- Patients that require a dose delay of > 28 days due to a cause unrelated to study participation will have the opportunity to continue study if deemed eligible to do so by the Protocol Chair of the study.

Patients who discontinue from the study for a study-related adverse event (AE) or an abnormal laboratory value must be followed at least once a week for 4 weeks and subsequently at 4-week intervals, until resolution or stabilization of the event, whichever comes first, except specifically mentioned.

Idasanutlin dose level reductions				
Starting dose	First reduction	Second reduction	Third reduction	Fourth reduction
200 mg	150 mg	100 mg	50 mg	Discontinue
150 mg	100 mg	50 mg		Discontinue
100 mg	50 mg	Discontinue		

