Grade 4							
Pulmonary (Cob	imetinib or Atezolizumab)						
	Mild-to-moderate events of pneumonitis have been reported with atezolizumab and						
Comoral	cobimetinib. All pulmonary events should be thoroughly evaluated for other commonly						
General guidance	reported etiologies such as pneumonia/infection, lymphangitic carcinomatosis, pulmonary embolism, heart failure, chronic obstructive pulmonary disease, or pulmonary hypertension.						
guidance	For events concerning for pneumonitis, consider comprehensive infectious evaluation						
	including viral etiologies.						
D	Continue atezolizumab and cobimetinib.						
Pneumonitis,	Re-evaluate on serial imaging.						
grade 1 (asymptomatic)	Consider patient referral to pulmonary specialist.						
(asymptomatic)	For recurrent pneumonitis, treat as Grade 3 or 4 event.						
	Withhold atezolizumab and cobimetinib.						
	Refer patient to pulmonary and infectious disease specialists and consider bronchoscopy						
	or BAL.						
D :::	• If bronchoscopy is consistent with immune-related etiology, initiate treatment with 1–2						
Pneumonitis,	
 
mg/kg/day oral prednisone or equivalent.
 
Resume atezolizumab and cobimetinib if event resolves to Grade 1 or better within 12
 
						
grade 2	Resume alezolizumab and codimetinib ii event resolves to Grade 1 or better within 12 weeks.						
	
 
Permanently discontinue atezolizumab and cobimetinib and contact Medical Monitor if
 
						
	event does not resolve to Grade 1 or better within 12 weeks.						
	For recurrent events, treat as a Grade 3 or 4 event.						
	Permanently discontinue atezolizumab and cobimetinib.c						
	Refer patient to pulmonary and infectious disease specialists and consider bronchoscopy						
	or BAL.						
Pneumonitis,	
 
If bronchoscopy is consistent with immune-related etiology, initiate treatment with 1−2
 
						
grade 3/4	mg/kg/day oral prednisone or equivalent.						
	If pulmonary event does not improve within 48 hr or worsens, consider adding an						
	immunosuppressive agent (e.g., infliximab, cyclophosphamide, IV lg, or mycophenolate						
	mofetil).  • If event resolves to Grade 1 or better, taper corticosteroids over ≥ 1 month.						
	The event resolves to Grade 1 of Detter, taper conticosteroids over 2 1111011th.						

Hepatic (Cobimetinib	or Atezolizumab)

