# 8.6. Special Considerations

- For toxicities which are considered by the treating investigator unlikely to develop into serious or life-threatening events (e.g. alopecia, altered taste etc.), treatment may be continued at the same dose without reduction or interruption.
- The treating investigator may reduce a subject's dose for a toxicity of any grade/duration where s/he believes it to be in the best interests of the subject.
- Any consideration to modification of the above dose modification guidelines should be discussed with the Principal Investigator for approval or disapproval in advance.
- □ If a toxicity requiring Cobimetinib or Idasanutlin permanent drug interruption occurs, Atezolizumab can be continued as a single-agent
- ☐ If a toxicity requiring Atezolizumab permanent drug interruption occurs, patients will come off both study drugs

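### The hold and stopping rules in 7.11, 8.4.2.10, 8.5 and 8.6 contradict each other for cobimetinib, for atezolizumab, and on whether atezolizumab stops with its partner drug

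*Combined protocol and SAP*

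**What the plan says.** **Cobimetinib.** The cobimetinib rules in 8.5 read: "If a patient requires a dose delay of > 28 consecutive days from the intended day of the next scheduled dose of Cobimetinib", due to study-related interventions, "then the patient must be discontinued from the study treatment". A delay for an unrelated cause may be excused by the Protocol Chair. In the toxicity tables of 8.5, the Grade 2 pneumonitis row says: "Resume atezolizumab and cobimetinib if event resolves to Grade 1 or better within 12" weeks. The rule for symptomatic LVEF decrease holds cobimetinib for at least 4 weeks and then allows it to resume. The hepatic row for AST/ALT above 3 x ULN with bilirubin above 2 x ULN restarts both drugs once laboratory and steroid conditions are met. Neither of these two gives an upper time limit.

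**Atezolizumab.** Section 7.11 lists among the reasons for ending protocol treatment: "Patients that require a dose delay of > 28 days. If the delay is due to a cause unrelated to study participation", the patient may continue under conditions. No drug is named. The atezolizumab rules in 8.5 say: "If Atezolizumab is held because of AEs for > 12 weeks beyond the scheduled date of infusion, the patient will be discontinued from Atezolizumab". They also require a steroid taper of at least 1 month before atezolizumab is resumed. Footnote a to the nephritis table in 8.4.2.10 says: "Atezolizumab may be withheld for a longer period of time (i.e., > 12 weeks after event onset"), by agreement between the investigator and the Study Chair.

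**Partner drug.** The idasanutlin rules in 8.5 say: "Patients who require dose reductions of Idasanutlin past the lowest dose level will be discontinued from study drugs treatment". The cobimetinib rules say the same of cobimetinib, and both sets take the patient off study treatment after a delay of more than 28 days. Section 8.6 says that after a toxicity requiring permanent interruption of either partner, "Atezolizumab can be continued as a single-agent". Section 7.11 adds that a patient needing reduction below dose level -1 should come off study unless benefit is judged to outweigh risk.

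**The concern.** These are operative instructions in the current text, and nothing says which prevails. In a multicenter trial, two investigators who each follow the protocol can reach opposite decisions on the same patient: one ends treatment, the other re-doses. That is first a safety matter.

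It also bears on interpretation. Section 24 asks whether adding cobimetinib or idasanutlin improves on a historical control of atezolizumab alone, judged by progression-free status at 16 weeks. A patient whose partner drug has stopped and who continues on atezolizumab is receiving the comparator regimen, yet still counts in the combination arm. If site interpretation decides who this happens to, the regimen behind the result is not fixed by the protocol.

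**Working it through.** No sample size, power or error rate is involved. The check sets the rules side by side, with unit conversions.

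**1. Cobimetinib: 28 days against 12 weeks**
- Limit in 7.11 and in the 8.5 cobimetinib rules: 28 days.
- Window in the Grade 2 pneumonitis row: 12 x 7 = 84 days; 84 / 28 = 3 times the limit.
- Test case: Grade 2 pneumonitis that resolves to Grade 1 six weeks after onset, 6 x 7 = 42 days. The 8.5 rule counts from the next scheduled dose. Cobimetinib is given on Days 1-21 of 28, so the longest wait for a scheduled dose is from Day 21 to Day 1 of the next cycle, which is 8 days. The delay is therefore at least 42 - 8 = 34 days, which exceeds 28. The drug rule ends study treatment; the table row resumes cobimetinib.
- The symptomatic LVEF rule has a minimum hold of 4 x 7 = 28 days, equal to the maximum delay elsewhere. The hepatic row suggests steroids with a taper of at least 1 month before restart, again with no upper limit.

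**2. Atezolizumab: limit and clock**
- 7.11: more than 28 days ends protocol treatment, with no drug named.
- 8.5: up to 84 days beyond the scheduled infusion. The mandatory taper of at least 1 month by itself uses about the whole 28-day allowance.
- 8.4.2.10 footnote: more than 84 days is possible, counted from event onset.
- The clocks differ. Infusions are 14 days apart. If an event starts 1 day after an infusion, 12 weeks from onset ends on day 1 + 84 = 85, and 12 weeks beyond the missed infusion ends on day 14 + 84 = 98. The gap is 13 days. The pneumonitis row states no starting point.

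**3. What stops with the partner drug**
- 8.5, cobimetinib and idasanutlin rules: a delay of more than 28 days, or a reduction past the lowest level, takes the patient off study treatment as a whole.
- 8.6: after a permanent partner stop for toxicity, atezolizumab may continue alone.
- 8.5 tables, Grade 2 (intolerable) or Grade 3 diarrhea and Grade 2 colitis: the partner must resume within 28 days or stop permanently, but atezolizumab may resume up to 12 weeks. An event that resolves between those limits leaves the patient on atezolizumab alone.
- 7.11: the benefit exception below dose level -1 has no counterpart in the 8.5 drug rules.

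**The case against.** Several points on the other side have force.

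- **Specific over general.** The atezolizumab rule in 8.5 can be read as qualifying 7.11, which names no drug. That is reasonable, but the text does not say so, and it cannot settle 8.5 against the nephritis footnote or the cobimetinib rule against the pneumonitis row.
- **Qualifiers.** The partner-drug rules apply to delays due to study-related interventions and excuse unrelated causes. The first phrase is undefined and could be read narrowly. But 7.11 carries no such restriction, and treatment-related pneumonitis is not a cause unrelated to participation, so the cobimetinib conflict remains.
- **LVEF.** This rule can be read as a decision made at 4 weeks, which would fit a 28-day limit. It is the weakest of the cobimetinib examples.

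A reader might also infer more than the documents support.

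- *That all three drugs may be resumed up to 12 weeks.* No row resumes idasanutlin after 28 days. For cobimetinib, the diarrhea, colitis and Grade 3 dermatologic rows keep 28 days and give 12 weeks to atezolizumab only.
- *That holds beyond 12 weeks are generally allowed.* The only express allowance is the nephritis footnote, for atezolizumab.
- *That every partner stop is in conflict.* The retinal vein occlusion row stops cobimetinib and continues atezolizumab, in line with 8.6.
- *That 7.11 permits dosing below the lowest listed level.* It states no such dose; remaining on atezolizumab alone is an equally available reading.
- *That the number affected can be estimated and set against the success threshold of 13.* Section 3.7.1.7 reports 34.8% treatment-related Grade 3-4 events for cobimetinib plus atezolizumab, but the clearest conflict concerns Grade 2 pneumonitis. The only such Grade 3-4 event in two or more patients was diarrhea (8.7%), where the cobimetinib window already agrees with the 28-day rule.

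**Conclusion.** The concern holds for three contradictions: the cobimetinib hold, the atezolizumab hold (limit and clock), and whether atezolizumab stops with its partner. The 28-day against 12-week conflict does not extend to resuming idasanutlin; the partner-stop conflict covers both arms.

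The size can be stated only as a difference between rules: 28 against 84 days for cobimetinib, and 28, 84 or more than 84 days for atezolizumab, on clocks that can differ by up to about two weeks. Subtracting 28 from 84 to get a common window of conflict is not valid, because the starting points differ or are not given. The documents give no frequency for such holds.

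The two-stage design (16 then 17 patients per arm, 13 or more successes) is unaffected. Patients who stop without progression continue to be scanned until progression (Study Calendar, note 7), and treatment deviations do not remove them from the analysis (section 25). What is at stake is consistent patient management and which regimen the 16-week result describes. This should be corrected.

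**What to change.** The sponsor should reconcile, in one amendment, sections 7.11, 8.4.2.10 (nephritis footnote), 8.5 (drug-specific rules for all three agents, symptomatic LVEF rule, Grade 2 pneumonitis row, combined transaminase and bilirubin row, diarrhea and colitis rows) and 8.6, so that:

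- each drug has one stated maximum hold, with a defined starting point, to which the other sections refer;
- each stopping rule names the drug or drugs that stop, in place of general references to study treatment or study drugs;
- the exception in 7.11 for reduction below dose level -1 and the drug rules in 8.5 give the same answer.

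Which limit or rule applies is a clinical decision for the sponsor; this review takes no position on it. The cost is amendment wording and site notification, with no new procedures and no additional patients.
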